The relationship between *PIK3CA* mutation and responsiveness of ER+ breast cancers to CDK4/6 inhibitors has not been investigated. In preclinical studies, PD0332991 was found to be effective in a subpopulation of both *PIK3CA* mutant and wild type cancer [88]. The most promising predictors of response identified in preclinical studies have been the presence of intact Rb or down regulation of p16; however, this has not been confirmed in the recently reported clinical trial of letrozole in combination with PD 0332991 as first line therapy for metastatic ER+ breast cancer [22]. Since *PIK3CA* mutation is an important driver event in ER+ breast cancer, and direct inhibitors of PI3K, including those that target specifically the alpha catalytic subunit, are being developed to treat tumors with *PIK3CA* mutation, it is important to investigate the anti-tumor effect and predictors of response to PD 0332991 in *PIK3CA* wild type and mutant population separately.

The study was designed initially to focus on the population of ER+ breast cancer without *PIK3CA* hotspot mutations since trials of inhibitors against PI3K pathway, such as the NCI9170, were ongoing the same time for the population with *PIK3CA* hotspot mutations. As the NCI9170 trial that enrolls patients with *PIK3CA* mutant tumors is approaching its enrollment target as of November 2013, we plan to open the *PIK3CA* mutant cohort for this trial, starting in institutions that do not have NCI9170 open.

1.8 Rationale for Adding Adjuvant PD 0332991 in Combination with Anastrozole in Patients who Derived benefit from the Addition of PD 0332991 during Neoadjuvant Therapy (Amendment #7)

Between 4/23/2013 and 4/24/2015, the study enrolled 50 patients with clinical stage II or III ER+ HER2- breast cancer to the *PIK3CA* mutant and *PIK3CA* wild type (WT) cohorts. Of these 50 patients, 45 (*PIK3CA* WT, n=28; *PIK3CA* mutant, n=15; *PIK3CA* unknown, n=2) were evaluable for Ki67 analysis at C1D15 after completion of 6 weeks of anastrozole and 2 weeks of PD 0332991 (for the primary endpoint). The data was presented at 2015 SABCS {Ma, 2015 #3841}. Complete cell cycle arrest (CCCA) was achieved in 39 of the 45 (87%, 90% CI: 75-94%) evaluable patients, 22 of 28 (79%, 90% CI: 62-90%) patients

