2.0 OBJECTIVES

Since surgery occurs 3 to 5 weeks following the last dose of PD 0332991 in order to avoid complications related to PD 0332991-induced myelosuppression, we propose to assess the primary endpoint of complete cell cycle arrest (Ki67 \leq 2.7%) on C1D15 while patients are receiving PD 0332991. The value of Ki67 on C1D15 and at surgery will provide data on the potential reversibility of Ki67 decrease when off PD 0332991 for at least 3 weeks. These data may help to hypothesize regarding the duration of the biologic effect of PD 0332991.

Amendment #5:

Please note that as of Amendment #5, a fifth cycle of daily PD 0332991 (consisting of 10-12 days of treatment, plus continued daily anastrozole) is added prior to surgery based on preliminary analysis of the first 18 patients showing an increase in tumor Ki67 at the time of surgery which was performed 3 to 5 weeks after the last dose of PD 0332991 (Cycle 4 Day 21). This data indicates that PD 0332991 has a reversible effect on cell cycle arrest. However, alternative explanations exist—for example, the emergence of resistance clones. To investigate these possibilities, we propose to re-initiate PD 0332991 (and continue anastrozole) for patients whose blood counts and other AEs recover sufficiently after 4 complete neoadjuvant cycles of PD 0332991 + anastrozole, and treat for an additional 10 to 12 days, with the last dose of PD 0332991 and anastrozole being administered on the day before surgery. Based on previous phase I studies, the mean ANC within 10-12 days of treatment is between 2.2 k-4.2 k/mcL (personal communication with Pfizer), therefore we expect majority of our patients will be able to complete Cycle 5. In fact, a neoadjuvant study consisting of 14 days of aromatase inhibitor +/- PD 0332991 before surgery is ongoing, and none of the first 9 patients randomized to receive PD 0332991 had ANC < 1,000 on Day 10 (personal communication with Pfizer).

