2.2 Secondary Objectives

1. To determine the rate of complete cell cycle arrest, defined by Ki67 $\leq 2.7\%$, following 2 weeks (C1D15) of neoadjuvant PD 0332991 in combination with anastrozole in women with clinical stage II or III ER+/HER2- breast cancer with PIK3CA hot spot mutation.
2. To determine the rate of complete cell cycle arrest, defined by Ki67 $\leq 2.7\%$, following 2 weeks (C1D15) of neoadjuvant PD 0332991 in combination with anastrozole in women with clinical stage II or III ER+/HER2- endocrine-resistant breast cancer.

The following objectives will be assessed in PIK3CA mutant cohort and in PIK3CA Wild Type (WT) cohort combined or separately, and assessed separately in the endocrine resistant cohort.

3. To compare the rate of complete cell cycle arrest between C1D1 and C1D15

4. To assess Ki67 level on serially collected tumor specimens (baseline, C1D1, C1D15, and surgery)
5. To determine the rate of PEPI 0 score with the study drug therapy
6. To determine the pathologic complete response (pCR) rate of study drug therapy
7. To assess the rate of clinical response and radiologic response in the neoadjuvant setting
8. To determine the safety profile (on therapy and post 30 days of therapy completion) of the study therapy during 4 months of neoadjuvant therapy.
9. To determine the safety profile of the study therapy during 2 years of adjuvant therapy.
10. To assess the long term outcomes of patients treated in this trial.

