15.5 Data Analysis

All data analyses will be performed separately for each cohort unless otherwise specified.

Demographic and clinical characteristics of the sample, as well as response, toxicity by grade, and loss to follow-up will be summarized using descriptive statistics. The rate of complete cell cycle arrest will be calculated and the corresponding 90% confidence interval (CI) will be provided. The rates for pCR and PEPI 0 and their 90% CIs will also be calculated. The differences in overall survival (OS) and relapse-free survival (RFS) for patients with or without complete cell cycle arrest on C1D1 will be described using Kaplan-Meier product limit estimator and compared by log-rank tests. Similar analysis will be performed for complete cell cycle arrest on C1D15 or patients with or without PEPI 0, with the two cohorts combined or separately. A trajectory analysis (see below) will also be performed for this comparison.

Analysis of other secondary endpoints:

Clinical response rate: The clinical response rate will be estimated by the number of patients whose disease meets the WHO criteria of complete or partial response prior to surgery divided by the total number of eligible patients who began combination neoadjuvant treatment. A 90% confidence interval for the true clinical response rate will be calculated using the Duffy-Santner approach for the endocrine resistant cohort (2-stage design). The complete cell cycle arrest rates and the corresponding 90% confidence intervals will also be calculated for PIK3CA wild type and mutant cohorts separately and combined.

Radiological response rate: The radiological response rate will be estimated by the number of patients whose disease meets with WHO criteria for complete or partial response at the evaluation prior to surgery divided by the total number of eligible patients who began

combination neo-adjuvant therapy. A 90% confidence interval for the true radiographic response rate will be calculated using the Duffy-Santner approach. The analysis will be performed with the two cohorts separately and combined.

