Adverse Events: All eligible patients that have initiated treatment will be considered evaluable for assessing adverse event rate(s). The maximum grade for each type of adverse event will be recorded for each patient using the NCI-CTCAE v4.0, and frequency tables will be reviewed to determine patterns. Additionally, the relationship of the adverse event(s) to the study treatment will be taken into consideration.

Ki67 suppression on Cycle 1 Day 1, Cycle 1 Day 15 and surgery: Following the approach of Dowsett et al. [26], the percent change in the Ki67 level from baseline will be determined on the log scale. A 95% t-confidence interval for the mean percent change in the Ki67 level from baseline will be constructed (if appropriate). The rate of complete cell cycle arrest on C1D1, C1D15, and surgery will be described by contingency tables compared by McNemar tests. Using trajectory analysis, we will also assess the association between distinct patterns of Ki67 change over time and clinical outcomes. Specifically, trajectory groups will be formulated to describe clusters of individuals with similar temporal patterns of Ki67 over time using finite mixture models with SAS procedure TRAJ. This method enables identification of the number of discrete trajectory types, and characterization of the shape and estimation of the prevalence of each type. We will choose the best models based on statistical tests (including Bayesian and Akaike information criterion, each of which test goodness-of-fit) and clinical judgment.

To assess the long term outcomes of patients treated in this trial: The long-term outcomes (i.e., pathologic complete response (pCr), local and distant recurrence, etc, as defined in section 12.4) will also be assessed in the PIK3CA wild and mutnt cohorts (separately and combined) and the endocrine resistant cohort, respectively. The categorical outcome will be summarized using contingency tables and compared by Fisher's exact test, while the time-to-event outcomes will be described using Kaplan-Meier product limit estimators and compared by log-rank test.

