15.6 Correlative Studies

Tumor cell apoptotic index: Apoptosis studies based on the TUNEL assay conducted in the context of the IMPACT study showed that the rate of apoptosis actually *declined* after two weeks of anastrozole treatment when the percentage TUNEL positive cells was less than one percent, with an SD of less than one percent [12]. Given the very low background of TUNEL positivity, a modest sized study is sufficient to demonstrate an increase in cell death. We will use the TUNEL assay to assess apoptosis at baseline and in the sample taken on PD 0332991. The TUNEL-positive cells will be counted using the point counting approach used for Ki67 and the apoptosis index will be calculated as the number of positive cells divided by the number of all cells and multiplied by 100.

Steady state levels of estradiol: Steady state levels of estradiol on serially collected serum samples will be examined in premenopausal women to confirm the efficacy of the

anastrozole goserelin therapy in suppressing both ovarian and peripheal estradiol production. The change of estradiol level over time will be described by summary statistics and also compared using 2-way ANOVA for repeated measurement data

Pharmacodynamic markers and markers of tumor cell senescence: The pharmacodynamic effect of PD 0332991 in combination with anastrozole on RB phosphorylation and markers of senescence will be assessed by phosphoproteomics and immunohistochemistry analysis on serial tumor biopsies. The change of RB phosphorylation and senescence markers over time will be described by summary statistics and also compared using 2-way ANOVA for repeated measurement data.

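### Surgical samples mix women on PD 0332991 with women 3 to 5 weeks off it, and Sections 15.5 and 15.6 never separate them

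*Combined protocol and SAP*

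**What the plan says.** Section 15.5 sets the general rule: "All data analyses will be performed separately for each cohort unless otherwise specified". For arrest it adds: "The rate of complete cell cycle arrest on C1D1, C1D15, and surgery will be described by contingency tables compared by McNemar tests". For PEPI 0: "The rates for pCR and PEPI 0 and their 90% CIs will also be calculated". Section 15.6 says of the tissue markers: "The change of RB phosphorylation and senescence markers over time will be described by summary statistics", followed by a two-way repeated-measures ANOVA whose second factor is not named. Section 2.2 lists serial Ki67, including the surgical sample, as secondary objective 4 and the PEPI 0 rate as objective 5. The only alternative grouping it gives is "assessed in PIK3CA mutant cohort and in PIK3CA Wild Type (WT) cohort combined or separately". Section 15 does not mention Cycle 5 or time since the last dose.

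Exposure at surgery is described elsewhere. Under Sections 5.1 and 5.2, a woman who receives Cycle 5 has surgery on Day 11 to 13 of that cycle, with the last dose planned for the day before. Under Sections 5.1, 6.4 and 10.2, a woman who does not receive Cycle 5 has surgery 3 to 5 weeks after the last dose. The Amendment 5 note in Section 2.0 gives the reason for Cycle 5: a "preliminary analysis of the first 18 patients showing an increase in tumor Ki67 at the time of surgery", at a time when surgery followed 3 to 5 weeks off drug. The note reads this as a reversible drug effect, names resistant clones as an alternative, and adds Cycle 5 to investigate.

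**The concern.** The surgical sample measures two different things. In a woman who completed Cycle 5, it shows whether arrest persists under continued drug. In a woman after washout, it shows whether arrest survives withdrawal. Pooled, the surgical arrest rate and the C1D15-to-surgery comparison depend on the share of women who received Cycle 5, and that share is set by calendar date and by recovery of counts and toxicity.

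The question behind Amendment 5 needs the two groups kept apart. The Ki67 trajectory groups in 15.5 have the same weakness: they may partly reproduce drug exposure instead of tumour biology. Section 1.9.4 still argues that comparing surgery with C1D15 will show irreversible arrest and senescence, on the premise that surgery is always at least 3 weeks off drug. That premise is false for women on drug at surgery.

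**Working it through.** **The plan's own design figures.** Exact binomial for 33 women, success at 20 or more, 44% versus 66%: alpha 0.041, power 0.801. Simon design (12 then 37 women, 5% versus 20%): alpha 0.093, power 0.902, early stopping 54% and 7%. All agree with Section 15.3. They concern arrest at C1D15 and are not in dispute. No precision or power is stated for any surgical analysis.

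**Inputs from the documents.** In Section 1.8, "Complete cell cycle arrest (CCCA) was achieved in 39 of the 45" evaluable women in the PIK3CA cohorts at C1D15: 22 wild type, 15 mutant and, by subtraction, 39 - 22 - 15 = 2 unknown. Section 2.0: at least 18 women had surgery off drug, cohort not stated.

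**Assumptions.** All 18 belong to the 45, so the Cycle 5 share is at most (45 - 18)/45 = 60%. For the paired comparison, all 18 are among the 39 arrested, leaving 39 - 18 = 21 in Cycle 5, and no woman gains arrest. The numbers losing arrest and the on/off rates are illustrative.

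**1. The pooled rate follows the mix.** Pooled rate = off + s × (on - off), where s is the share on drug.
- On 80%, off 40%: s = 0 gives 40%; s = 0.60 gives 0.40 + 0.60 × 0.40 = 64%.
- On 70%, off 50%: s = 0 gives 50%; s = 0.60 gives 0.50 + 0.60 × 0.20 = 62%.

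**2. The pooled McNemar test cannot see where arrest is lost.** With k losses and no gains, the exact two-sided p is 2 × 0.5^k. The difference is the proportion losing arrest, washout minus Cycle 5, with a Newcombe 90% interval.

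| Losses | McNemar p | All in washout | Spread over both groups |
|---|---|---|---|
| 6 | 0.031 | 6/18 vs 0/21: +33 points (15 to 53) | 3/18 vs 3/21: +2 (-17 to 23) |
| 9 | 0.0039 | 9/18 vs 0/21: +50 points (29 to 68) | 4/18 vs 5/21: -2 (-23 to 21) |
| 12 | 0.0005 | 12/18 vs 0/21: +67 points (44 to 82) | 6/18 vs 6/21: +5 (-19 to 28) |

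The middle column is the pattern expected from reversal off drug. The last shows arrest also lost on drug. Each row has one p-value for both.

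**3. The chance of detecting a loss also follows the mix.** A separate simulation used 45 pairs, 3% background change in each direction, and a 50% chance of losing arrest for each off-drug pair. Power of the exact McNemar test at two-sided 5% was about 1.00 with everyone off drug, 0.85 with half on drug, and near 0 with everyone on drug. With a 30% chance of loss it was 0.92, 0.41 and near 0.

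**4. PEPI 0 and tissue markers.** PEPI 0 requires residual-tumour Ki67 of 2.7% or less (Section 1.9.6), so exposure enters through that component. The documents do not allow the effect to be computed. RB phosphorylation and senescence markers are to be assayed at all time points (Section 1.9.4), so the surgical value mixes both states.

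**The case against.** The strongest reply is that the effect is unquantified and its reach narrow. McNemar's test uses only discordant counts, so equal p-values for different splits would arise for any subgroup in any paired analysis. The 18/21 split and the on/off rates are not in the documents. The primary endpoint is untouched, the markers are exploratory, the PIK3CA cohorts are closed, and in the open cohort most women are expected to complete Cycle 5. Any comparison would be non-randomised, in small cells and, for the closed cohorts, added after enrolment. Section 15.5 also lists three time points without naming pairs, trajectory groups might pick out women whose Ki67 rebounds, the second ANOVA factor is unnamed, and Section 1.9.4 is background text.

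The points on size and precision stand, and they limit the fix to description. They do not remove the problem. This is not an arbitrary subgroup: it is the exposure the protocol changed in order to study Ki67 at surgery. McNemar tests across C1D1, C1D15 and surgery naturally include C1D15 versus surgery, a comparison Section 1.9.4 intends for Ki67 and the markers. Trajectory groups do not identify drug exposure, and an unnamed ANOVA factor cannot be read as adjusting for it.

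**Conclusion.** The concern holds and should be addressed. As written, 15.5 and 15.6 average two different quantities in the surgical Ki67, arrest and marker analyses, in proportions set by calendar date and recovery, and cannot address the question Amendment 5 raised. The true size is unknown. Under the stated assumptions the pooled surgical arrest rate could move by 12 to 24 points as the Cycle 5 share goes from 0 to 60%, and one McNemar p-value is compatible with a between-group difference of +50 points or of about zero. PEPI 0 is affected only through Ki67, by an amount that cannot be computed. The C1D15 primary endpoint and the decision rules in Section 15.3 are unaffected.

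**What to change.** - In 15.5 and 15.6, report surgical Ki67 and arrest, PEPI 0, and RB/senescence markers by Cycle 5 receipt (on drug at surgery versus washout). Do this within the endocrine resistant cohort and within the combined PIK3CA cohorts, and by single PIK3CA cohort where numbers allow.
- List separately women who stopped Cycle 5 early or stopped before completing Cycle 4, and give days since the last PD 0332991 dose.
- Show the C1D15-to-surgery change in each group as an estimate with a 90% interval. Compare groups by the difference in the proportion losing arrest, with its interval, not by setting two McNemar p-values side by side.
- Name the second factor of the two-way ANOVA.
- Label the comparison descriptive, non-randomised and, for the closed cohorts, added after enrolment.
- Reconcile 1.9.4 with 5.1 and 5.2, so that the irreversibility inference uses only women off drug at surgery.

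The cost is SAP wording and two-group tables from data already collected on the treatment and surgery forms and in the pill diary. No sample size or decision rule changes. The price is precision. In the illustration the exact 90% interval for loss of arrest is 13 to 37% with 9/39 but 29 to 71% with 9/18. In the mutant cohort (15 arrested, assumed 7 and 8), losses of 2/7 and 2/8 give +4 points with interval -31 to 38. In the endocrine resistant cohort, a 20% arrest rate in 37 women is about 7 arrested (37 × 0.20 = 7.4), so loss of arrest there would be a listing. The split informs the reversibility question but cannot settle it.

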9.1.3 Sample Collection and Schedule in the Neoadjuvant Setting (Endocrine Resistant Cohort)

All sample collection is mandatory.

Correlative Study	Blood / Tumor	Type of Tube	Volume to Collect	Time point	Process at Site?	Temperature Conditions for Storage / Shipping
Tumor for research♣	Core biopsies	2 cores in OCT 2 cores in 10% formalin	14-G core needle	Pre-PD0332991, C1D15, Surgery*	No	Cores in OCT should be immediately frozen; cores in formalin should be stored / shipped at ambient temperature
Plasma for research	Whole blood	EDTA (purple)	10 mL	Pre-PD0332991, C1D15, Surgery	Yes	-80°C
Serum for research	Whole blood	Clot-tube (red)	10 mL	Pre-PD0332991, C1D15, Surgery	Yes	-80°C
Germline DNA for research	Whole blood	EDTA (purple)	10 mL	Pre-PD0332991	No	Ambient, same-day shipment (avoid Friday blood draw)
Whole blood for plasma circulating DNA	Whole blood	Cell-free DNA BCT	10 mL x2	Pre-PD0332991, C1D15, Surgery	No	Ambient, same-day shipment (avoid Friday blood draw)

Pre-PD0332991: C1D1

♣ Tumor collection prior to PD0332991 is not required for the endocrine resistant cohort if the patient had undergone research tumor collection as part of the tumor biopsy for the Ki67 analysis prior to registration to this trial. Consent to research of archival tumor specimens collected prior to and during this trial is required for all patients.

* Additional surgical tumor specimens are required; please refer to instruction 'g' below

Instructions for sample collection and processing:

Note that sample collection/shipment kits are available for the study.

- a: For biopsies at each time point: 4 cores (14 G core needle) will be taken at each time point, with 2 in 10% formalin and 2 freshly frozen in OCT. Care needs to be taken to reduce the ischemic time to as much as possible to less than 30 min.
- b: A repeat biopsy may be needed in consented patients if the first biopsy did not yield enough tumor cells for Ki67.
- c: Samples can be obtained at the time of surgery. Care needs to be taken to reduce the ischemic time to as much as possible to less than 30 minutes.

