10.2 Neoadjuvant Study Treatment Calendar (ALL Cohorts)

	≤ 14 days prior to registration	C1D1 ^A	C1D15 ±1 day	C2-5 D1±3 days	3 (+/-1) days prior to surgery	Off Study - Progression	Surgery ^B	Post-surgery ^C
TREATMENT								
Anastrozole ^E		Daily until the day of surgery (if no progression)						
Goserelin ^E		Every 28 days (if no progression)						
PD 0332991 ^F		3 weeks on and 1 week off ^{G,T}			D/C			
CLINICAL ASSESSMENT								
H&P, PS	X	X		X		X		X
Clinical meas. of breast lesions ^J	X	X		X		X		Exam
Adverse event assessment	X	X		X		X		X
CBC + differential	X			X	X ^Y			X
Serum chemistry ^K	X			X				X
Serum pregnancy test ^L		X			X	X		
Drug compliance assessment				X				
EKG (lead II) ^N	X						X	
RADIOLOGY								
Mammogram and US of breast and axillary masses ^O	X ^H			X ^H		X		
SAMPLE COLLECTION								
Tumor biopsies ^R		X ^W	X ^P	X ^Q		X ^S	X	
Research blood ^R		X ^U	X ^{P,V}			X ^S	X	

- A. C1D1 office visit, labs, EKG, as well as pre-PD 0332991 tumor biopsies may be done within 14 days prior to C1D1.
- B. Please refer to section 5.1. Surgery occurs between Cycle 5 day 11 and day 13 in patients who received Cycle 5 treatment. In patients who did not receive Cycle 5 treatment, surgery occurs 3 to 5 weeks following the last dose of PD 0332991.
- C. 30-60 days post-surgery, then yearly to document recurrence and survival for 5 years.
- E. Anastrozole (and goserelin if premenopausal) should have been started at least 28 days prior to C1D1 **(only applies to PIK3CA Mutant and Wild Type cohorts).
- F. Patients will keep a pill diary (Appendix D).
- G. If C1D15 Ki67 is > 10%, patient will discontinue PD 0332991 and be observed for AEs 30-60 days following the last dose, then followed per protocol. Further treatment is at the discretion of the treating physician.
- H. Prior to start of PD 0332991 (within 12 weeks prior to registration) and at the end of cycle 4 before surgery.
- J. 2D measurements of the breast lesion should be performed. Using a standard cm calibrated caliper, tape or ruler, the longest axis and the perpendicular axis of the tumor are to be measured and recorded in metric notation. In patients with synchronous lesions, it is recommended that both lesions be measured and biopsied the same if they are both >1cm with at least one dimension; otherwise, the dominant mass is followed clinically and by Ki67

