- K. Serum chemistry is albumin, alkaline phosphatase, total bilirubin, bicarbonate, BUN, calcium, chloride, creatinine, glucose, potassium, total protein, SGOT/AST, SGPT/ALT, sodium
- L. In premenopausal women only
- N. EKG will be performed at baseline, pre-surgery, and as needed. Surgery may be delayed if QTc prolongation has occurred.
- O. Mammogram and ultrasound of the diseased breast must be completed within 12 weeks prior to registration. Imaging studies must include bidimensional breast tumor measurements, but retrospective measurement is allowed in the study.
- P. C1D15 biopsy and blood draw may be done up to C1D20 for scheduling convenience, although C1D15 is strongly preferred.
- Q. Optional biopsy on C2D15, C3D15, or C4D15 in patients with indeterminate Ki67 on C1D15 biopsy or who missed the C1D15 biopsy.
- R. Research funded. Research blood samples are mandatory except where indicated.
- S. Optional
- T. If counts recover within 3 weeks of the end of C4, re-start PD 0332991 for 10 to 12 doses (C5) (last dose to be the day before surgery).
- U. PKs to be drawn on a day prior to initiation of PD 0332991 (may be C1D1) pre-anastrozole and again 90 minutes post-anastrozole. Other research blood include serum, plasma, whole blood for germline DNA and whole blood for circulating tumor DNA is also collected on C1D1. Details are described in Section 9.1.2. PK samples are not required in the endocrine resistant cohort.
- V. PKs to be drawn pre-dose of both drugs and again 90 minutes post-dose of both drugs. PK samples are not required in the endocrine resistant cohort.
- W. Not required in endocrine resistant cohort if a research biopsy was performed prior to registration or an archival tumor block is available
- Y. Only required in patients who are in Cycle 5.

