12.0 MEASUREMENT OF EFFECT

12.1 Neoadjuvant Treatment

Complete cell cycle arrest: This is defined as $\text{Ki67} \leq 2.7\%$, which will be assessed at C1D1, C1D15, and surgery. In patients without C1D15 Ki67, Ki67 on D15 of subsequent cycles could be used instead.

Clinical Evaluation: Prior to Cycle 0 (or performed during pre-registration for study NCI 9170), and at the end of each neoadjuvant treatment cycle cycles (that is, at the end of Cycles 1-4) the longest axis and the perpendicular axis of the measurable lesion should be measured and recorded in metric notation by tape, ruler or caliper technique on the case report forms.

Radiologic evaluation of tumor size: Mammogram and ultrasound imaging will be performed prior to Cycle 0 (or performed during pre-registration for study NCI 9170) and at the end of Cycle 4 combination therapy for bidimensional measurement of the tumor.

WHO criteria will be used to assess clinical and radiologic responses.

Complete Response (CR) is defined as the disappearance of all known disease based on a comparison between the pre-treatment measurements and the measurements taken at the completion of neo-adjuvant therapy (that is, at the end of cycle 4 neo-adjuvant combination therapy). In addition there is no appearance of new lesions.

Partial Response (PR) is defined as a 50% or greater decrease in the product of the bi-dimensional measurements of the lesion (total tumor size) between the pre-treatment measurements and the measurements taken at the completion of neo-adjuvant therapy (that is, at the end of cycle 4 neo-adjuvant combination therapy). In addition there can be no appearance of new lesions or progression of any lesion.

No Change (NC): a 50% decrease in total tumor size cannot be established nor has a 25% increase in the size of the lesion been demonstrated.

Progressive Disease (PD): A 25% or greater increase in the total tumor size of the lesion from its pretreatment measurements or the appearance of new lesions.

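### Does the waived pre-drug biopsy invalidate the C1D1 arrest comparisons in the endocrine-resistant cohort?

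*Combined protocol and SAP*

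**What the plan says.** Objective 3 in section 2.2 compares the arrest rate at C1D1 with that at C1D15 and is to be assessed separately in the endocrine-resistant cohort. Section 15.5 sets the default, "All data analyses will be performed separately for each cohort unless otherwise specified", and names the test: "The rate of complete cell cycle arrest on C1D1, C1D15, and surgery will be described by contingency tables compared by McNemar tests". It also plans Kaplan-Meier and log-rank analyses of "The differences in overall survival (OS) and relapse-free survival (RFS) for patients with or without complete cell cycle arrest on C1D1".

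Entry to this cohort (section 3.4.1) requires Ki67 above 10%, by central testing or central slide review, after at least two weeks of neoadjuvant endocrine therapy. Arrest is Ki67 of 2.7% or less (section 12.1).

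On the pre-drug sample, the note to the table in section 9.1.3 reads "Pre-PD0332991: C1D1". The same section adds that "Tumor collection prior to PD0332991 is not required for the endocrine resistant cohort if the patient had undergone research tumor collection" as part of the qualifying biopsy. The calendar in section 10.2 gives a wider waiver in footnote W: "Not required in endocrine resistant cohort if a research biopsy was performed prior to registration or an archival tumor block is available". Its footnote A says that "pre-PD 0332991 tumor biopsies may be done within 14 days prior to C1D1".

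For the other visit, section 12.1 gives a fallback: "In patients without C1D15 Ki67, Ki67 on D15 of subsequent cycles could be used instead". It gives none for C1D1.

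**The concern.** A woman whose pre-drug biopsy is waived has no separate C1D1 sample. If her qualifying value stands in, it exceeds 10% and can never count as arrest. Her only possible discordant pair is then no arrest at C1D1 followed by arrest at C1D15. Her contribution to the McNemar test is fixed on one side by the entry rule, and a small p-value could be taken as evidence that PD 0332991 adds to endocrine therapy. Some of the apparent gain could also be regression to the mean, because the women were selected on a high reading. If the value is instead left missing, the pair drops out. The plan does not say which applies, so two analysts could report different p-values from the same data. In the OS/RFS comparison, the C1D1-arrest group could be very small or empty.

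**Working it through.** **Design check.** Section 15.3 gives 12 then 37 women, stopping at 0 arrests in stage 1 and declaring insufficient activity at 3 or fewer in total, with rates of 5% and 20%. The early-stop probability is (1 − p)^12: 0.95^12 = 0.540 and 0.80^12 = 0.069, matching the stated 54% and 7%. The exact probability of a positive result is 0.0935 at 5% and 0.902 at 20%, matching the stated alpha of 0.1 and power of 90%. All of this uses C1D15 alone.

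**McNemar test with no reverse pairs.** Let c be the number of women with arrest at C1D15 only, and b the number with arrest at C1D1 only. With b = 0, the uncorrected chi-square is (c − b)²/(c + b) = c on 1 df. The exact two-sided p is 2 × 0.5^c, capped at 1. Section 15.5 names no version, sidedness or alpha, so both are shown.

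| c | uncorrected p | exact p |
|---|---|---|
| 1 | 0.317 | 1.0 |
| 3 | 0.083 | 0.25 |
| 4 | 0.046 | 0.125 |
| 5 | 0.025 | 0.063 |
| 6 | 0.014 | 0.031 |
| 7 | 0.008 | 0.016 |

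**Carried in or dropped.** Take 7 arrests in 37 (19%, near the 20% target) and assume no C1D1 arrest among women with a fresh biopsy. Carried in, c = 7 and p = 0.008 / 0.016. Dropped, with 2 of the 7 arrests in waived women, c = 5 and p = 0.025 / 0.063. With 4 of the 7, c = 3 and p = 0.083 / 0.25. The documents do not give the waived share or how the arrests divide.

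**Rejection when nothing changes between visits.** Assumptions: n = 37, true arrest rate q at both visits, visits independent within a woman, two-sided 0.05 level, no stage-1 stop. If all are waived and carried in, c is binomial(37, q). The uncorrected test rejects at c of 4 or more, the exact test at 6 or more. The other rows come from enumerating the paired counts.

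| Waived share | q = 5%: uncorrected / exact | q = 10% | q = 20% |
|---|---|---|---|
| none | 3.8% / 0.3% | 4.7% / 1.5% | 4.3% / 2.4% |
| half | 4.9% / 0.4% | 12% / 3.7% | 20% / 13% |
| all | 11% / 1.0% | 51% / 16% | 96% / 78% |

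Two readings of this table matter:

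- With every woman waived, the uncorrected threshold of 4 arrests is the same count as the design's go threshold. The 11% at q = 5% is the 9.3% alpha without the stage-1 stop. The test repeats the primary result.
- The large figures sit at q = 20%, the rate the combination is hoped to reach. For that to be the no-change rate, endocrine therapy alone would have to produce it in women selected as resistant to endocrine therapy.

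**C1D1-arrest group for OS/RFS.** Even if all 37 women had a fresh biopsy, the expected size is 37 × q, or 1.9 at 5% and 7.4 at 20%. With 18 fresh biopsies (about half, assumed) it is 18 × q, or 0.9 to 3.6. The chance that it is empty is (1 − q)^18, or 40% at 5%, 15% at 10% and 2% at 20%. The comparison is weak mainly because the cohort is small and selected for high Ki67; the waiver makes it weaker.

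**The case for a change.** The strongest case for a change is that sections 1.1 and 1.9.1 give the comparison of anastrozole alone with the combination a real purpose, and a C1D1 zero set by eligibility cannot inform it. The p-value moves several-fold with an unwritten rule, a reader of a table may not see why, and a few sentences would settle it. Prior therapy in this cohort may also be any endocrine agent, so for some women the paired change is not the effect of PD 0332991 alone.

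Part of this stands. No section defines the C1D1 value for a waived woman. The waiver in section 9.1.3 is narrower than footnote W in section 10.2. Under the stand-in reading the test carries no information beyond the C1D15 count, and regression to the mean is a fair caveat.

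The rest does not carry a change. Section 9.1.3 equates the pre-drug sample with C1D1, and footnote A accepts samples up to 14 days old. A qualifying biopsy inside that window is therefore already a valid pre-drug sample, and only older or archival tissue is unclear. The qualifying reading is a measurement, not an imputation: a woman above 10% was not in arrest when sampled. The mixed prior therapy is disclosed in section 3.4.1.

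Restricting the C1D1 analyses to women with a second, separate biopsy would discard valid in-window samples and keep a subset that may not represent the cohort, possibly leaving no usable comparison. Statisticians could reasonably differ on that trade.

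Whether the OS/RFS analysis was meant for this cohort is also arguable. The next sentence in section 15.5 speaks of two cohorts, which suggests the PIK3CA pair, although the by-cohort default can be read to include this one.

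**Conclusion.** No change to the plan follows. The gap is an unwritten definition in a secondary analysis that has no stated alpha and no decision attached. An analyst can fill it sensibly by using the pre-drug on-endocrine reading, stating its source and the number of pairs, and noting that zero arrest at C1D1 follows from the entry rule.

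On that reading, at the design's 5% null rate with all 37 women waived, the exact test rejects 1% of the time and the uncorrected test 11%. Higher rates depend on arrest rates and a waived share that the documents do not give. The difference between the waiver conditions is a drafting inconsistency about tissue collection.

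The go rule in section 15.3, the C1D15 arrest rate with its 90% confidence interval, and this cohort's adjuvant eligibility in section 3.5.1 (C1D15 Ki67 of 10% or less) do not use the C1D1 value. This conclusion would be weaker if the McNemar p-value were presented as independent evidence of a drug effect; nothing in the plan gives it that role.
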